6.2 Medical history

Medical history will be coded using the latest version of Medical Dictionary for Regulatory Activities (MedDRA) and summarized by system organ class (SOC) and preferred term (PT) by treatment arm and total. A patient will be counted only once for multiple events within each SOC/PT. Medical History, including a detailed ophthalmic history reported prior to dosing, will be listed by patient.

6.3 Prior and concomitant medications

Prior medication is the medication that patient stopped taking prior to screening visit. Concomitant medication is the medication that patient continued taking or took from screening visit through end of study. Prior and concomitant medications will be coded using the latest version of World Health Organization (WHO) Drug Dictionary and summarized by Anatomical Therapeutic Chemical level 4 (ATC4) and preferred term (PT) by study arm and total. A patient will be counted only once for multiple events within each ATC4 and PT. Prior and concomitant medications will be summarized in table form. Listings of prior and concomitant medications will also be provided.

7. Efficacy Analysis

7.1 Secondary endpoints

The following continuous secondary efficacy endpoints will be analyzed using mixed models for repeated measures (MMRM):

- Change in BCVA from Baseline to Weeks 12, 24, and 48
- Change in CST from Baseline to each study visit as assessed by SD-OCT and read by a Reading Center
- Area under the curve (AUC) of change from baseline of CST for each study visit
- Area under the curve (AUC) of change from baseline of BCVA for each study visit

The MMRM will be used for the primary analysis of the change from baseline in BCVA, which is based on the ETDRS VA chart assessed at a starting distance of four meters. The model will include the change from baseline at Day 2, Week 1 to Week 48 as the dependent variable, and the independent variables will include continuous BCVA baseline, categorical treatment arm

(active or sham), categorical study visit, and arm-by-visit interaction. Within-subject correlation will be modeled using subject-specific random intercepts. The model will assume a compound symmetry covariance structure. If there are convergence problems with this model, then other covariance structure may be fitted. The primary analysis will be limited to data collected prior to or on the rescue date. A supportive analysis will be performed for all data collected, regardless of rescue therapy. Subjects who violated major inclusion or exclusion criteria will be excluded from the primary and supportive analyses.

When BCVA outliers occur, a sensitivity analysis excluding the outliers will be performed. If deemed appropriate, other sensitivity analyses may also be considered to assess the impact of outliers.

The change from baseline in CST, as assessed by SD-OCT and read by a Reading Center, AUC of change from baseline in BCVA and CST, will be analyzed using MMRM, same as the analysis of BCVA.

The following binary secondary efficacy endpoints will be summarized:

- Proportion of patients who require 2 or more, or 1 or more anti-VEGF rescue over 12, 24, and 48 Weeks
- Proportion of patients without macular fluid at Weeks 12, 24, and 48 as assessed by SD-OCT

Proportion of patients who require 2 or more, or 1 or more anti-VEGF rescue over 12, 24, and 48 Weeks will be summarized for each treatment group. Confidence intervals of difference in proportions between treatment groups will be calculated using an exact method (Chan and Zhang, 1999) implemented in the SAS procedure Freq. Criteria for rescue therapy are worsening of CST by 75 μ m relative to Baseline and/or a 10-letter decrease in BCVA compared to peak BCVA from Baseline. Patients who meet rescue criteria can be rescued with anti-VEGF treatment. Rescued patients will continue with study visits per protocol. Proportion of patients without macular fluid at Weeks 12, 24, and 48 as assessed by SD-OCT will be analyzed using same method.

BCVA and SD-OCT data will be listed.

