Inclusion criteria for last anti-VEGF given was changed from between 3 and 5 weeks prior to day 1, to between 3 and 6 weeks prior to day 1 [Section 4.5 Inclusion Criteria]	Matching the time from last anti-VEGF injection to best capture response sensitivity (i.e., long enough from last anti-VEGF injection to avoid anti-VEGF induced inhibition of activity but short enough to avoid re-emergence of active neovascularization and inflammation). This increases the likelihood of differentiating between UBX1325 and sham treated patients. Furthermore, the window of 3–6 weeks might better capture standard visit timing for patients and clinic.
Revised inclusion criteria to allow patients with PDR DME (ETDRS-DRSS Score at 65C [or DR severity level of 8] or less severe) to participate in this study [Section 4.5 Inclusion Criteria]	Based on preclinical animal studies and impact on neovascularization, there is sufficient data to support the hypothesis that there could be a potential effect of UBX1325 on PDR patients.
Stratification by anti-VEGF treatment agents [Section 6.2 Method for Assigning Patients to the Treatment Group]	To obtain a balance between UBX1325 and sham treatment arms with regards to prior anti-VEGF agents.
Established that a formal interim analysis will occur at 12 weeks [Section 8.7 Planned Interim Analysis]	Revised the plan for analysis to reflect a planned interim analysis at 12 weeks after a certain proportion of patients meet the 12-week timepoint as will be determined in the SAP. Based on UBX1325-01 data, we believe study drug effects may be seen earlier at 8–12 weeks. This is also to ensure the safety and well-being of patients at 12-week timepoint.

Area of Change	Rationale
Changed rescue criteria from "worsening	To better align with the standard practices followed
CST by 100 µm from Baseline (Day 1) per	by the treating physician.
SD-OCT or a 10-letter decrease in BCVA	
compared to peak BCVA from Baseline	
(Day 1)" to "worsening CST by 75 µm from	
Baseline (Day 1) per SD-OCT and/or a	
10-letter decrease in BCVA compared to	
peak BCVA from Baseline (Day 1)"	
[Section 5.1.10 Rescue Criteria]	

The following summarizes the principal elements requiring that change be made to the protocol. Other minor modifications for administrative purposes have been made to provide clarity and are captured in the redlined document.

The	princi	nal com	popents o	f change t	to the	study are	described	in th	ne table b	elow

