posterior vitreous detachment and surgical induction of a vitreomacular separation might improve DME. With the advent of optical coherence tomography (OCT), vitreomacular adhesion was shown to be a riskfactor for DME (Browning et al., 2018). A controversy exists regarding the effects of vitrectomy for DME. Some reports suggest that vitrectomy reduces macular thickening but does not improve VA, yet others report improved VA and decrease in macular thickening. Prospective, randomized clinical studies have not been conducted to evaluate the effect of vitrectomy on diverse DME patient population. Nonetheless, there is a general acceptance that vitrectomy hasa role in the management of at least some cases of DME (Browning et al., 2018).

Studies have shown the safety and efficacy of IVT anti-VEGF treatments in patients with DME, some of which were the basis for Food and Drug Administration (FDA) approval of anti-VEGF therapies for the treatment of DME (Elman et al., 2010; Nguyen et al. 2012; Brown et al., 2015). The Diabetic Retinopathy Clinical Research Network (DRCR) net trial, Protocol T, was a 660-patient study comparing 3 IVT anti-VEGF treatments in patients with DME, followed for 2 years of treatment. Focal/grid laser was added if DME persisted and was not improving at 6 months or later. Results showed that focal/grid laser was administered as a supplement in 41%, 64%, and 52% of aflibercept, bevacizumab, and ranibizumab groups, respectively. From Baseline to 2 years, mean VA letter score improved by 12.8 with aflibercept, 10.0 with bevacizumab, and 12.3 with ranibizumab. Treatment group differences varied by baseline VA (Wells et al. 2016).

A meta-analysis published by Virgili et al., 2018 concluded that anti-VEGF treatments are effective at improving vision in patients with DME with 3 to 4 in every 10 patients likely to experience an improvement of 3 or more lines VA at 1 year. Aflibercept may confer some advantage over ranibizumab and bevacizumab in patients with DME at one year in visual and anatomic terms, but it is unclear whether this applied to the long-term. Overall, the safety profile between the 3 anti-VEGF drugs, aflibercept, ranibizumab, or bevacizumab is similar (Virgili et al., 2018).

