6.2 Method for Assigning Patients to the Treatment Group

After a patient has been identified as potentially eligible for the study, the patient will be invited to participate. If the patient agrees to study participation, written informed consent

will be obtained before any study-specific procedures are performed. Patients who have consented to participate in the study will be assigned a unique number.

After the patient has been consented and completed all screening procedures confirming eligibility, they may proceed to Day 1, where they will be randomized in a 1:1 ratio to UBX1325 or sham arm, stratified by most recent anti-VEGF treatment that patients received prior to Day 1. There will be two strata: 1) aflibercept vs 2) ranibizumab or bevacizumab. Patients will be randomly allocated to receive treatment through the randomization system, which administers the randomization code generated by the Sponsor's biostatistician or designee. Following receipt of the treatment assignment, the site staff will prepare the Study Drug as instructed by the Pharmacy Manual.

Patients who are randomized but do not receive treatment may be replaced.

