2.1 Trial design

This is a Phase 2a, prospective, randomized, double-masked sham-controlled two-arm clinical trial. Patients will be randomized in a 1:1 ratio to UBX1325 or sham arm, stratified by most recent anti-VEGF treatment that patients received prior to Day 1. There will be two strata: 1) aflibercept vs 2) ranibizumab or bevacizumab. Each patient will be administered a single 50 μ L UBX1325 IVT injection or sham procedure on Day 1 and be followed for up to 54 weeks (6-week screening period + 1 dose day + 24-week follow-up period + 24-week extended follow-up period). This is a multicenter trial that plans to enroll patients at approximately 32 sites in the U.S. and Canada. A study schematic is shown below (Figure 1 from the study protocol). Schedule of visits and assessments is presented in Appendix A.

Figure 1 Schematic of Phase 2a Proof-of-Concept Study

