7.2 Exploratory endpoints

Exploratory endpoints include

- Change from Baseline in Diabetic Retinopathy Severity Scale (DRSS) score at Weeks 24 and 48
- Change in capillary perfusion from Baseline to Weeks 12, 24, and 48 as assessed by Optical Coherence Tomography Angiography (OCT-A) and Fluorescein Angiography (FA)

Change from Baseline in DRSS score will be presented as the proportion of patients with a \geq 2step improvement in diabetic retinopathy (DR) severity from baseline on the ETDRS DRSS at Weeks 24 and 48. The proportion of patients with a \geq 2-step improvement in diabetic retinopathy (DR) severity from baseline will be analyzed using the analysis method following those for the binary secondary efficacy endpoints.

For change in capillary perfusion from Baseline to Weeks 12, 24, and 48, the analysis method will follow those for the continuous secondary efficacy endpoints.

Key parameters of OCT-A and FA will be summarized, and all OCT-A, FA and CFP data will be listed.

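### The MMRM leaves out the anti-VEGF stratum used in randomisation; if that stratum is prognostic, standard errors are slightly too wide

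*SAP*

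**What the plan says.** Protocol 6.2 and SAP 2.1 both randomise 1:1 with stratification. The Protocol states "There will be two strata: 1) aflibercept vs 2) ranibizumab or bevacizumab", and SAP 2.1 gives the same two strata. The Protocol's summary of changes gives the reason for introducing them: "To obtain a balance between UBX1325 and sham treatment arms with regards to prior anti-VEGF agents".

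Protocol 8.5 leaves the details of the MMRM to the SAP. SAP 7.1 says of that model that "the independent variables will include continuous BCVA baseline, categorical treatment arm" ("active or sham), categorical study visit, and arm-by-visit interaction"). The list ends there, with no stratum term. SAP 7.1 applies the same model to change in CST and to the AUC of change in BCVA and CST. For capillary perfusion, SAP 7.2 says "the analysis method will follow those for the continuous secondary efficacy endpoints".

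Nothing elsewhere restores the term. The stratum is not among the SAP 7.3 subgroups. SAP section 10 lists two departures from the protocol, and neither concerns it. No reason for leaving it out is given.

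**The concern.** When allocation is stratified, the arms are made alike on the stratum, so differences between strata contribute little or nothing to the sampling variation of the treatment contrast. A model without the stratum still counts those differences as residual noise. If the stratum is prognostic, the reported standard error therefore exceeds the true one, confidence intervals are too wide and tests reject less often than their nominal level.

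Precision is what is at stake. The treatment estimate is not biased and false positives are not inflated. Even so, change in BCVA is the first secondary endpoint and the basis of the sample size. With 62 patients, the study reached 80% power only by accepting a two-sided level of 0.15.

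The stratum could matter here. Patients enter 3 to 6 weeks after their last anti-VEGF injection, and Protocol 5.1.10 defines rescue by that same last agent. The supportive analysis in SAP 7.1 keeps data after rescue, so any difference between agents could enter those outcomes.

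**Working it through.** **Inputs.** From SAP 2.4 (same figures in Protocol 8.2): difference 8 letters, SD 13, drop-out 5%, 31 per group, two-sided level 0.15. Evaluable patients per arm: 31 × 0.95 = 29.45. The documents give no stratum effect, stratum split or block scheme, so those are assumed below. SD 13 is treated as the SD after baseline adjustment.

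**The plan's own figure.** A two-sample t-test has power 0.7999 with 28 per arm and 0.811 with 29, so 29 evaluable per arm are needed. 29/0.95 = 30.5, rounded up to 31 per arm, 62 in total. The stated size reproduces. At 29.45 per arm the power is 0.816.

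**Formulas.** Let R² be the share of outcome variance explained by the stratum beyond baseline, with balanced arms.
- Reported SE / true SE = 1/sqrt(1−R²).
- Real level of a nominal 0.15 test = 2 × (1 − Φ(1.4395/sqrt(1−R²))).
- Power: noncentral t with noncentrality 8 / (13 × sqrt(1−R²) × sqrt(2/29.45)). The critical value is t/sqrt(1−R²) with the stratum omitted and t with it included.
- Gap in letters between two equal strata that gives this R²: 2 × 13 × sqrt(R²).

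| Assumed R² | Gap (letters) | SE too wide by | Real level | Power, omitted | Power, included |
|---|---|---|---|---|---|
| 0 | 0 | 0 | 0.150 | 0.816 | 0.816 |
| 1.2% | 2.8 | 0.6% | 0.148 | 0.817 | 0.820 |
| 5% | 5.8 | 2.6% | 0.140 | 0.822 | 0.832 |
| 10% | 8.2 | 5.4% | 0.129 | 0.828 | 0.848 |
| 15% | 10.1 | 8.5% | 0.118 | 0.835 | 0.864 |

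**Which row is plausible.** The only between-agent data are in Protocol 2.2: "mean VA letter score improved by 12.8 with aflibercept, 10.0 with bevacizumab, and 12.3 with ranibizumab". Stratum 2 pools the last two agents, so the gap from aflibercept depends on their mix:
- all ranibizumab: 12.8 − 12.3 = 0.5 letters, R² = (0.5/26)² = 0.04%;
- half and half: 12.8 − 11.15 = 1.65 letters, R² = (1.65/26)² = 0.4%;
- all bevacizumab: 12.8 − 10.0 = 2.8 letters, R² = (2.8/26)² = 1.2%.

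These are two-year gains on continued treatment, so they are only a rough guide.

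**Simulation, single visit** (100,000 runs, N = 60, permuted blocks of 4 within two equal strata assumed):
- R² 5%: null rejection 0.140 omitted, 0.150 included; power 0.825 and 0.835.
- R² 10%: null rejection 0.128 and 0.148; power 0.834 and 0.853.
- R² 10% with strata split 30/70: null rejection 0.131 and 0.150; power 0.834 and 0.854.
- Without blocking within strata, null rejection with the stratum omitted stays at 0.150 to 0.151. The conservatism depends on balance.

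**Simulation, repeated measures** (4,000 runs per setting, 29 per arm, 11 visits, compound symmetry with assumed correlation 0.6, complete data, equal strata):

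| Gap (letters) | Model SE / empirical SD, omitted | Null rejection, omitted | Model SE / empirical SD, included | Null rejection, included |
|---|---|---|---|---|
| 0 | 1.003 | 0.148 | 1.003 | 0.149 |
| 6 | 1.017 | 0.139 | 0.990 | 0.152 |
| 10 | 1.061 | 0.120 | 0.981 | 0.150 |

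With 4,000 runs, the Monte Carlo error is about 0.006 on a rejection rate near 0.15 (sqrt(0.15 × 0.85/4000)). Direction and size agree with the formulas.

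**The case against.** The strongest reply is that this is a convention with almost no consequence here. No passage promises a stratum-adjusted analysis, and allocation alone can deliver the balance that stratification was introduced for. On the documents' own figures the cost is negligible: with an even mix of ranibizumab and bevacizumab in stratum 2, the standard error is 0.2% too wide. R² of 10% or 15% needs a gap between strata of 8.2 or 10.1 letters, more than the 8-letter treatment effect the trial is sized on. The primary endpoint is safety and is summarised descriptively.

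All of that stands, and it is why the point is minor. The 10% and 15% rows show how the error grows; nothing in the documents supports them.

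A second objection concerns the power gains, which come from an idealised single-visit test with complete data. The actual model pools Day 2 to Week 48, and its primary version stops at rescue, so fewer patients may contribute late and balance within strata may erode. A constant stratum term also captures only part of a difference that develops over time. The captured share is (mean of f)² / mean of f², where f is the size of the difference at each of the 11 scheduled visits relative to its maximum. A difference that rises linearly to Week 48 gives about 54%; one that plateaus at Week 12 gives about 73%. This also stands: the tabulated gains are closer to an upper limit than a forecast.

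Neither objection gives a reason to leave the term out. It costs one degree of freedom, and with R² = 0 the power stays at 0.816.

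**Conclusion.** The concern holds as a minor one. The omission can be read directly from SAP 7.1 and affects every continuous efficacy endpoint. Its consequence is conditional. If the stratum predicts outcome beyond baseline and allocation is balanced within strata, standard errors are too wide and tests conservative. If it is not prognostic, there is no loss.

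On the between-agent figures in Protocol 2.2, the standard error is at most about 0.6% too wide and adjustment gains about 0.2 points of power. An assumed R² of 5% would give 2.6% and 1.0 point. These sizes rest on SD 13, 29.45 evaluable patients per arm, equal strata and balanced allocation, and the block scheme is not stated. They also set aside the compound symmetry assumption ("The model will assume a compound symmetry covariance structure"), a separate matter that could move the standard error either way.

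**What to change.** In SAP 7.1, add the two-level randomisation stratum (aflibercept versus ranibizumab or bevacizumab), as recorded in the randomisation system, as a fixed effect in the MMRM for BCVA. State that it carries over to CST, both AUC endpoints and capillary perfusion.

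The cost is one sentence and one degree of freedom, with no new data to collect. Fixing the term in advance also removes any choice about adding it after unmasking. A stratum-by-visit term is optional. It would capture a difference that changes over time, but with 11 post-baseline BCVA visits it adds 11 − 1 = 10 further parameters, so the main effect alone is a reasonable default in a trial of this size.

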4.5 Inclusion Criteria

To be included in this study, each individual must satisfy all of the following criteria:

- 1. Patients aged \geq 18 years.
- 2. DR (PDR and NPDR) patients with DME (ETDRS-DRSS Score at 65C [or DR severity level of 8] or less severe as determined by a Central Reading Center), who had at least 2 anti-VEGF intravitreal (IVT) injections (one or more of the following agents: aflibercept, bevacizumab or ranibizumab) in the preceding 6 months prior to Day 1, with the last anti-VEGF given between 3 and 6 weeks prior to Day 1.
- 3. Center-involved DME with central subfield thickness (CST) \ge 300 µm on SD-OCT at Screening as determined by a Central Reading Center.
- 4. BCVA in the study eye (most affected) of 73 to 20 ETDRS letters (equivalent to 20/40 to 20/400 on the Snellen chart) at Screening and at Day 1. If both eyes are equal, then it's Investigator discretion.
- 5. $IOP \le 23$ mmHg in the study eye on Day 1.
- 6. Clear ocular media and adequate pupillary dilation to permit CFP and adequate BCVA evaluation.
- 7. Patients who have the capacity to give informed consent and who are willing and able to comply with all study-related procedures and assessments.

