5.1.3 Medical History and Concomitant Medication Review

A detailed medical history will be obtained by the Investigator or qualified designee. This will include a comprehensive medical history and a complete review of systems, with specific attention to inclusion and exclusion criteria. The use of anti-VEGF for both eyes in the preceding 6 months prior to Screening should be documented in the concomitant medication log. All historical imaging and visual acuity assessments when available for both eyes in the preceding 6 months prior to Screening should be entered into the designated eCRF. Past medical history deemed by the Investigator as not clinically relevant to the patient's overall health status or to his or her DME will not be captured. Relevant medical history will be recorded in the electronic case report form (eCRF).

All medications taken will be recorded in the eCRF Concomitant Medication Log. Medical History and Concomitant Medication Review should log should be performed at each study visit.

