3.2. Study Day and Baseline

Study Day 1 is defined as the day UBX1325 injection or sham procedure is administered. Subsequent days are numbered consecutively (*i.e.*, Day 2, Day 3) and are calculated as: visit date - dosing date + 1. Before Day 1, study days are numbered sequentially with negative values (*i.e.*, Day -1, Day -2) and are calculated as: visit date - dosing date. There is no Day 0.

Baseline value will be the last measurement taken on or before the date of UBX1325 injection or sham procedure administration. It will be taken from the pre-dose assessment on Day 1 unless otherwise noted.

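### Time since the last anti-VEGF injection (3 to 6 weeks at entry) is used in no efficacy model, stratum, subgroup or specified baseline table; the cost is a little precision, not bias

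*SAP*

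**What the plan says.** - **Entry window.** Protocol section 4.5, criterion 2, requires prior anti-VEGF treatment "with the last anti-VEGF given between 3 and 6 weeks prior to Day 1". SAP section 2.2 gives the same window.
- **Reason for the window.** The protocol's summary of changes explains the window now in force. The interval should be "long enough from last anti-VEGF injection to avoid anti-VEGF induced inhibition of activity but short enough to avoid re-emergence of active neovascularization and inflammation", and this is expected to help separate UBX1325 from sham.
- **Baseline.** SAP section 3.2 says of the baseline value: "It will be taken from the pre-dose assessment on Day 1 unless otherwise noted". Each patient's baseline therefore falls 3 to 6 weeks after the previous drug.
- **Model.** In SAP section 7.1 "the independent variables will include continuous BCVA baseline, categorical treatment arm", then "categorical study visit, and arm-by-visit interaction". No other term is listed. Change in CST and the AUCs of BCVA and CST "will be analyzed using MMRM, same as the analysis of BCVA".
- **Other places the interval could appear.** Randomisation is stratified by the most recent agent, not its timing (protocol 6.2, SAP 2.1). The SAP 7.3 subgroups are baseline BCVA, CST, DR severity and HbA1c. SAP 6.1 names no such baseline variable, and SAP 6.3 summarises medications by class and preferred term. The binary endpoints are compared without covariates.
- **Data.** Protocol section 5.1.3 states: "The use of anti-VEGF for both eyes in the preceding 6 months prior to Screening should be documented in the concomitant medication log". It then requires every medication taken to be entered in the same log.

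**The concern.** Two patients with the same Day 1 BCVA may be at different points after their last anti-VEGF dose. One injected three weeks earlier may still be partly supported by that drug and lose letters as it wears off. One injected six weeks earlier may already have lost that support. Their expected changes from Day 1 would then differ whatever the trial treatment. Baseline BCVA cannot fully stand in for the interval, because eligible scores run from 20 to 73 letters for many other reasons.

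If so, a predictor known before randomisation is left in the residual, and nothing guards against the two small arms differing in it by chance. There is a second route. Rescue is judged from Day 1 CST and from peak BCVA (protocol 5.1.10), and the primary BCVA analysis keeps data only up to rescue. The interval could therefore also affect whose data stop early, though the documents do not allow this to be quantified.

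**Working it through.** **Inputs from the documents** (protocol 8.2, SAP 2.4): difference 8 letters, SD 13, two-sided alpha 0.15, power 80%, dropout 5%, 31 per arm. The window of 3 to 6 weeks is from protocol 4.5.

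**Assumed, because the documents give no figure:** the interval is uniform over the window, and change in BCVA shifts by 1, 2 or 3 letters per week of interval (3, 6 or 9 letters across the window).

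**Step 1: reproduce the sample size.** Normal approximation: n per arm = 2 × (1.440 + 0.842)² × 13² / 8² = 27.5, so 28. The t-test needs 29. Then 29 / 0.95 = 30.5, rounded up to 31 per arm, or 62 in total. The stated figure reproduces.

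**Step 2: precision as planned.** Completers per arm = 31 × 0.95 = 29.45. SE of the arm difference = 13 × √(2/29.45) = 3.39 letters. Power = Φ(8/3.39 − 1.440) = 82.2%.

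**Step 3: chance imbalance in the interval.** SD of a uniform 3-week range = 3/√12 = 0.866 week. SE of the difference in arm means = 0.866 × √(2/29.45) = 0.226 week. The 95% limit = 1.96 × 0.226 = 0.44 week.

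**Step 4: effect on the arm difference, and gain from adjustment.** Shift = slope × 0.44. R² = (slope × 0.866)² / 169. Adjusted SE = 3.39 × √(1 − R²). Power is recomputed as in step 2.

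| Assumed slope (letters/week) | 95% limit of chance shift (letters) | R² | Adjusted SE (letters) | Power |
|---|---|---|---|---|
| none | 0 | 0 | 3.39 | 82.2% |
| 1 | 0.4 | 0.4% | 3.38 | 82.3% |
| 2 | 0.9 | 1.8% | 3.36 | 82.7% |
| 3 | 1.3 | 4.0% | 3.32 | 83.4% |

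For scale, the smallest difference significant at 0.15 is 1.44 × 3.39 = 4.9 letters. The shifts are 95% limits; the typical (one SD) shift is about half as large. A different spread of intervals would scale the shifts in proportion to its SD.

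**Step 5: cost of the covariate.** BCVA has 11 post-baseline visits (Visits 2 to 12). The planned model has 1 intercept + 1 baseline + 1 arm + 10 visit + 10 arm-by-visit = 23 fixed-effect parameters. A continuous main effect adds 1. Main effect plus visit interaction adds 11, in 62 patients whose primary data stop at rescue.

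**The case against.** The strongest reply is that a randomised comparison does not need this term. Allocation is 1:1, so the interval is balanced in expectation. Any chance imbalance is ordinary sampling error, already inside the SD of 13 and the model's standard error. That stands. A reader might infer that an imbalance would pass as a UBX1325 effect, beyond what the test allows for. The documents do not support that reading. What remains is narrower: once a particular imbalance has occurred, an adjusted estimate corrects for it and an unadjusted one does not.

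A reader might also take the protocol to say that baselines sit on a waning drug effect of known importance. It does not. The rationale says the window was chosen to avoid both residual inhibition and re-emergence, which is itself design control, and it gives no size for any change within the window. Steep slopes are hard to credit: 6 letters per week would mean 18 letters across the window, more than the design SD of 13.

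Three further points have force. Baseline BCVA is in the model and absorbs part of any effect. Carry-over should matter most in the early weeks, whereas the named BCVA endpoints are Weeks 12, 24 and 48. And this is a Phase 2a trial with a safety primary endpoint, in which one more covariate is optional.

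On the data, section 5.1.3 speaks of anti-VEGF use before Screening and does not literally mention dates. But the log covers all medications, including an injection during the 42-day screening period, and the entry window cannot be verified without the date.

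**Conclusion.** The omission is confirmed throughout the efficacy plan, and the sponsor's own window rationale makes the interval a reasonable covariate. The consequence is minor. At assumed slopes of 1 to 3 letters per week with a uniform interval, chance imbalance moves the arm difference by at most about 0.4 to 1.3 letters at the 95% limit, against 8. The interval explains about 0.4% to 4% of the variance, and adjusting for it adds about 0.1 to 1.2 points of power. These figures rest wholly on the assumed slopes and spread. They also treat 13 letters as the residual SD and apply one slope at every visit. No corresponding CST figure can be given from the documents, which state neither an SD nor a slope for CST. Neither bias nor a threat to the trial's conclusions is shown. The reason to act is that the value is fixed before randomisation and should already be available, and choosing it after unmasking would look data-driven.

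**What to change.** - In SAP section 7.1, add days from the last study-eye anti-VEGF injection to Day 1 as one continuous main-effect covariate in the BCVA, CST and AUC models. State that the date comes from the concomitant medication log.
- Prespecify the interval-by-visit interaction as a sensitivity analysis only. It allows for an effect that fades over time but costs 11 parameters in total.
- In SAP section 6.1, add a summary of the interval by arm.

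The cost is SAP wording, one degree of freedom in the main models, and a check that the log holds the injection date for the correct eye. The likely gain is small. The change does not adjust the binary rescue comparison, which has no covariates.
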